7.1. Adverse Event Definitions

7.1.1. Adverse Event

Adverse event: An adverse event is any unfavorable and unintended sign (including an abnormal laboratory finding), symptom, or disease (new or exacerbated) temporally associated with the use of a medicinal product, whether or not related to the medicinal product.

Events meeting the definition of an adverse event **include**:

- A worsening, excluding minor fluctuations, in the nature, severity, frequency, or duration of a pre-existing condition;
- Development of an intercurrent illness during the study;
- Development of symptoms that may or may not be related to the use of a concomitant medication or investigational product;
- Injury or accidents: If a medical condition is known to have caused the injury or accident, the medical condition and the accident should be reported as 2 separate medical events (eg, for a fall secondary to dizziness, both “dizziness” and “fall” should be recorded separately); and
- An investigational abnormality (eg, laboratory parameter, vital sign, ECG) only if the abnormality is considered clinically significant by the investigator based on at least one of the following criteria:
 - Induces clinical signs or symptoms;
 - Requires active intervention;
 - Requires interruption or discontinuation of study drug.

Events that **do not** meet the definition of an adverse event include:

- Medical or surgical procedures (eg, surgery, endoscopy, tooth extraction, transfusion); the condition that leads to the procedure is an adverse event;
- Pre-existing diseases or conditions present or detected before the start of study drug administration that do not worsen;
- Situations where an untoward medical event has not occurred (eg, planned hospitalization for an elective procedure, with elective defined as known or planned at the time of signing of the informed consent);
- Events of heavy menstrual bleeding, as heavy menstrual bleeding is quantified as an efficacy endpoint, unless meets seriousness criteria.

Adverse events that occur during the study should be evaluated by the investigator and graded according to Common Terminology Criteria for Adverse Events (CTCAE). Episodic adverse events, such as vomiting, or those that occur repeatedly over a period of consecutive days are “intermittent”. All other events are “continuous”. Additional information on detecting, documenting, and reporting adverse events and serious adverse events are provided below. No toxicity-related dose reductions of study drug are permitted, however, study drug can be held for a period of up to 2 weeks for evaluation and treatment of an adverse event. The study drug may be restarted if deemed safe for the patient by the investigator.

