1.1. Schedule of Activities

Table 1: Schedule of Activities for Study MVT-601-3003

PERIOD	OPEN-LABEL TREATMENT									SAFETY FOLLOW-UP
	VISIT NAME (Timing is relative to MVT-601-3001/-3002)	Week 24/Baseline (Week 24 of Parent Study; Baseline of Extension Study)	Week 28	Week 32	Week 36	Week 40	Week 44	Week 48	Week 52 ^a (or Early Termination of Study Drug)	
Visit Window (days)	Parent Study Day 169 - 10 to + 20	± 7	± 7	± 7	± 7	± 7	± 7	± 10	-	- 3 to + 18
Informed Consent	X ^d									
Review Eligibility Criteria	X									
Concomitant Medications ^e	X ^f	X	X	X	X	X	X	X	X	X
Vital Signs (BP, HR, Temperature)	X ^g	X	X	X	X	X	X	X	X ^h	X
Weight	X ^g			X				X	X ^h	
Complete Physical Examination	X ^g							X		
Visual Acuity ⁱ	X ^g									
Signs and Symptoms-Directed Physical Examination ⁱ		X	X	X	X	X	X		X ^h	X
12-Lead ECG ^k	X ^g							X	X ^h	
Clinical Laboratory Tests ^l	X ^{g,m}	X	X	X	X	X	X	X ^m	X ^h	X
Pharmacodynamics Sample ⁿ	X ^{g,m}							X ^m	X ^{h,m}	
Urinalysis	X ^g							X	X ^h	
Pregnancy Test (Urine)	X ^g	X	X	X	X	X	X	X	X ^h	X

PERIOD	OPEN-LABEL TREATMENT									SAFETY FOLLOW-UP
VISIT NAME (Timing is relative to MVT-601-3001/-3002)	Week 24/Baseline (Week 24 of Parent Study; Baseline of Extension Study)	Week 28	Week 32	Week 36	Week 40	Week 44	Week 48	Week 52 ^a (or Early Termination of Study Drug)	Un-scheduled ^b	Follow-Up ^c (~30 days after last dose of study drug)
Visit Window (days)	Parent Study Day 169 - 10 to + 20	± 7	± 7	± 7	± 7	± 7	± 7	± 10	-	- 3 to + 18
Transvaginal Ultrasound ^o	X ^g							X ^p	X ^h	
Bone Densitometry ^d	X ^g			X				X ^{p,r}	X ^h	
Endometrial Biopsy	X ^{g,s}							X ^p	X ^h	
Dispense Study Treatment	X	X	X	X	X	X	X		X ^h	
Patient Paper Diary ^t	X	X	X	X	X	X	X	X	X	
Dispense Feminine Products	X	X	X	X	X	X	X		X ^h	
Feminine Product Collection and Venous Blood Sample ^u	X ^g	X	X	X	X	X	X	X	X ^h	
Treatment Compliance		X	X	X	X	X	X	X	X ^h	
Take Study Drug Dose in Clinic ^v	X ^w							X	X ^h	
Daily Self-Administration of Study Treatment ^v		X								
MIQ ^x	X ^g	X	X	X	X	X	X	X	X ^h	X
UFS-QoL Questionnaire ^x	X ^g			X				X	X ^h	
EQ-5D-5L Questionnaire ^x	X ^g							X	X ^h	
Adverse Event Collection ^y	X ^z	X	X	X	X	X	X	X	X	X
Status of Menstruation Recovery										X ^{aa}

BP, blood pressure; ECG, electrocardiogram; EQ-5D-5L, European Quality of Life Five-Dimension Five-Level Scale; HR, heart rate; MIQ, Menorrhagia Impact Questionnaire; UFS-QoL, Uterine Fibroid Symptom and Health-Related Quality of Life

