6.3. Early Termination Visit and Follow-up Visit

All patients withdrawing from the study prior to Week 52 will complete an Early Termination visit. The Early Termination visit procedures are identical to those of Week 52; however, for patients whose last dose of study drug is during Week 32 or earlier, the following procedures do not need to be performed: transvaginal ultrasound (with or without a transabdominal ultrasound) and bone densitometry. These procedures may be performed, however, at the investigator's discretion, if they aid in follow-up of ongoing adverse events.

Patients (including those who complete the Week 52 visit and those who withdraw early from this study) will have a Follow-up visit approximately 30 days after the last dose of study drug, or prior to the date of initiation of another investigational agent or hormonal therapy affecting the hypothalamic-pituitary-gonadal axis or surgical intervention or other invasive procedure for uterine fibroids, whichever occurs first. However, for patients who enroll directly into another relugolix clinical study upon completion of the Week 52 visit, then the Follow-up visit may be waived.

The Follow-up visit will be used to assess safety after discontinuation of study treatment including adverse events, clinical safety laboratories, and return of menstruation. Refer to the Schedule of Activities (see [Section 1.1](#)) for individual study visit procedures during the Follow-up visit.

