6.5. Study Procedures

6.5.1. Efficacy-Related Procedures

6.5.1.1. Menstrual Blood Loss as Assessed by the Alkaline Hematin Method

The volume of menstrual blood loss is measured in milliliters using the alkaline hematin method [Hallberg, 1964]. The method involves pummeling used feminine products in a solution and measuring the resulting hematin absorbance against calibration curves. The method is validated in accordance with current FDA Guidance for Method Validations and is an accepted quantitative clinical endpoint for the assessment of heavy menstrual bleeding. The site staff will provide collection kits with standardized and validated feminine products to patients for the collection and assessment of those products to determine menstrual blood loss.

The feminine products will be dispensed and collected at each visit until the patient completes treatment or terminates participation from the study prior to completing treatment. The site must document the start and stop dates of the patient's menses corresponding to the collected feminine products. Each time the patient submits her feminine products from a menstrual cycle for analysis, a venous blood sample will be collected and sent to the laboratory. Details regarding materials, process, and requirements for the menstrual blood loss collection will be provided in the Study Reference Manual.

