7.2.1. Adverse Event Reporting Period

Adverse events and serious adverse events will be collected under this extension study protocol from the administration of the first dose of extension study drug until the Follow-up visit approximately 30 days after the last dose of study drug or the date of initiation of another investigational agent or hormonal therapy affecting the hypothalamic-pituitary-gonadal axis or surgical intervention for uterine fibroids, whichever occurs first, as also specified in the study Schedule of Activities ([Section 1.1](#)). Serious adverse events reported to the investigator after the

safety reporting period should be reported to the sponsor if the investigator assesses the event as related to the study drug treatment.

Reporting instructions for serious adverse events are provided in [Section 7.6](#).

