Baseline menstrual blood loss is defined as the average menstrual blood loss from the two Screening menstrual cycles used to meet the inclusion criteria prior to the date of the first dose of study drug in the parent study as assessed by the alkaline hematin method. The menstrual blood loss during the last on-treatment cycle (Week 52) is the total menstrual blood loss during the last 35 days on treatment as assessed by the alkaline hematin method.

Patients from Group C, who discontinue the extension study before Week 32 (28 days) will be considered non-responders.

For the endpoints of time to achieving a menstrual blood loss volume of < 80 mL AND at least a 50% reduction from parent study Baseline menstrual blood loss volume, time to event will be defined as weeks from randomization in the parent study to first occurrence of the event as assessed by the alkaline hematin method. Patients without an event will be censored at last assessment date prior to the end of study. Kaplan-Meier methods will be used to describe the time to event distributions for each parent study treatment arm.

Descriptive statistics will be provided for changes in menstrual blood loss, hemoglobin, Uterine Fibroid Scale – Symptom Severity, Menorrhagia Impact Questionnaire Score, Numerical Rating

Scale score for uterine fibroid-associated pain, uterine volume, and uterine fibroid volume to parent study Baseline.

For binary endpoints, the point estimate and 2-sided 95% CI for the proportion will be provided by parent study treatment group.

Details on the endpoint analyses including derivations, handling of missing data, and statistical methods will be provided in the SAP.

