7.2.2.3. Week 52/EOT Feminine Product Collection Interval

To ensure collection of all feminine products used during that menstrual cycle, an interval of up to 35 days for measurement of the primary endpoint was selected to accommodate women who continue to have cyclic bleeding on study treatment and whose natural cycle was at the upper end of the normal cycle duration range. This method is consistent with that used during screening for collection of feminine products and with that used for the primary efficacy analysis in the parent studies. Specifically, the feminine product collection interval at Week 52/EOT is driven by types of bleeding patterns experienced by the patients, as described below:

- For patients who continue to have cyclic bleeding, the length of the interval depends on the duration of the patient's natural cycle; this is consistent with the way the Baseline MBL volume was determined (eg, the interval ranging from approximately 21 to 35 days);
- Patients who report irregular, non-cyclic bleeding are instructed to collect and return all feminine product used between study visits, up to 35 days, as per the schedule of events;
- For patients who report amenorrhea on the feminine production collection eCRF page, an interval of last 35 days of treatment will be reviewed to ensure that reported amenorrhea is not due to incomplete collection.

For patients who are in the midst of an episode of cyclic bleeding at the time of the Week 52/EOT visit, the visit window may be extended up to 7 days after the last dose of study drug to ensure patients return all used feminine products over that bleeding episode.

Per protocol, all used feminine products are to be collected at each visit and returned for analysis using the alkaline hematin method. For patients who continue to have menstrual bleeding, study visits are timed such that the feminine products used in the entire menstrual bleeding cycle are collected in one container provided at each visit.

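### Non-serious heavy menstrual bleeding after the last dose is neither measured in mL nor reportable as an adverse event, and no summary of its severity is planned

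*Protocol*

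**What the plan says.** The file holds two protocol texts. The SAP states that it is based on Amendment 1, so section numbers here follow that text. The other text has the same wording on the points quoted below, although blood-loss measurement is 6.5.1.1 there and 6.6.1.1 in Amendment 1.

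- **Exclusion.** Section 7.1.1 names as not being adverse events: "Events of heavy menstrual bleeding, as heavy menstrual bleeding is quantified as an efficacy endpoint, unless meets seriousness criteria". No time limit is attached.
- **Measurement.** Section 6.6.1.1: "The feminine products will be dispensed and collected at each visit until the patient completes treatment or terminates participation". Section 9.4 defines the efficacy value: "The menstrual blood loss during the last on-treatment cycle (Week 52) is the total menstrual blood loss during the last 35 days on treatment".
- **Extension.** SAP Section 7.2.2.3 says that "the visit window may be extended up to 7 days after the last dose of study drug", but only for women with a cyclic bleed in progress at the Week 52/EOT visit.
- **Adverse event period.** Section 7.2.1 collects events "until the Follow-up visit approximately 30 days after the last dose of study drug", or to the start of another investigational agent, certain hormonal therapy or fibroid surgery if sooner.
- **Purpose of the last visit.** Section 6.3: "The Follow-up visit will be used to assess safety after discontinuation of study treatment including adverse events, clinical safety laboratories, and return of menstruation".

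**The concern.** Leaving the treated symptom out of the adverse event record is defensible while the same symptom is measured in mL at every visit. That is the only reason Section 7.1.1 gives. Once collection stops the reason lapses, but the exclusion continues to the end of adverse event reporting.

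This affects what the safety tables can show. If sites follow Section 7.1.1, the tables will contain no non-serious post-treatment heavy bleeding by definition. A reader could take that as a finding about stopping the drug when it is a consequence of the recording rule. The case that matters most is bleeding that comes back worse than before treatment. Section 7.1.1 would otherwise treat worsening of a pre-existing condition as an adverse event.

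**Working it through.** No sample size or event count is involved. The check sets the collection rules side by side and does day arithmetic on the visit window.

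**Length of the interval.** The Schedule of Activities (Section 1.1) places the Follow-up visit about 30 days after the last dose, with a window of -3 to +18 days.

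- Earliest visit: 30 - 3 = day 27. Latest visit: 30 + 18 = day 48.
- Where collection ends with the last dose, adverse event reporting outlasts it by 27 to 48 days.
- Where the SAP's 7-day extension is used in full, the interval is 27 - 7 = 20 to 48 - 7 = 41 days.

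These figures assume that reporting is not ended sooner by one of the events named in Section 7.2.1 or, under SAP Section 9.1, by entry into MVT-601-035. Protocol Section 6.3 lets the visit be waived for women who go directly into another relugolix study, while SAP Section 2.1 says women entering MVT-601-035 will have it. Those two statements need reconciling, but the interval exists for women who leave the programme either way.

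**What is collected in the interval**, from the Schedule and the procedure sections:

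- Feminine products: none dispensed at Week 52 and no collection marked at Follow-up, so no mL value.
- Paper diary: not marked at Follow-up.
- Adverse events: collected, but non-serious heavy menstrual bleeding is excluded.
- MIQ: marked at Follow-up. Item 1 grades the most recent period from light to very heavy. Section 6.6.1.5, however, speaks only of visits in the Open-Label Treatment period.
- Menses return: Section 6.6.2.7 records the date of the first menstruation, with a later telephone contact if it has not resumed. Neither gives an amount or grade.
- Blood count: marked at Follow-up, so one hemoglobin value.

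**What is summarised.** SAP Section 7.3.6 gives the MIQ as a listing by patient only. The tables in SAP Section 9.1 do not separate events with onset after the last dose. No planned output describes how heavy post-treatment bleeding was.

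**The case against.** The strongest reply is that the period is not blank. The MIQ at Follow-up asks directly how heavy the last period was, the date of first menses is recorded, and a blood count is taken. Section 6.6.2.4 makes abnormal, clinically significant laboratory results reportable as adverse events, and bleeding that meets a seriousness criterion stays reportable. A reader might infer that post-treatment bleeding goes entirely unrecorded, or that the trial cannot tell whether bleeding returns. The documents support neither reading: return of menstruation is a stated purpose of the visit and has its own procedure.

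A second reply is that every woman entered the parent studies with heavy bleeding (Section 4.3: at least 80 mL per cycle for two cycles, or at least 160 mL for one). Return to that state is the underlying disease, and a separate bullet in Section 7.1.1 already excludes pre-existing conditions that do not worsen. This stands. Recording all returning heavy bleeding as adverse events would conflict with that bullet, and much of it would be a non-event even without the contested exclusion. A reader might also want to put a number on the missing events, but the documents give no rate of post-treatment heavy bleeding and no number of women leaving the programme.

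A third reply is that the objectives concern up to 52 weeks of treatment, and that withdrawal is studied in MVT-601-035. That lowers the weight of the point. It does not remove it, because Section 6.3 assigns safety after discontinuation to this study's Follow-up visit. The sources named above also do not fill the gap. A date carries no severity, and one hemoglobin value is indirect, particularly as iron therapy is allowed (Section 5.9.2.2). The MIQ is only listed, its timing is stated inconsistently, and a woman whose menses has not returned would be answering about an earlier period.

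**Conclusion.** The point holds in a limited form. For 27 to 48 days after the last dose, or 20 to 41 days where the 7-day extension is used in full, non-serious heavy menstrual bleeding is not measured and cannot be an adverse event, even when it is worse than before treatment. The stated reason for the exclusion does not reach that interval, and no analysis summarises the severity of bleeding in it.

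The conclusion rests on sites applying Section 7.1.1 as written and on adverse event reporting running to the Follow-up visit. It concerns off-treatment safety reporting only; the primary endpoint and on-treatment adverse event counts are untouched. The number of events affected cannot be estimated from the documents.

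**What to change.** 1. **Protocol Section 7.1.1.** Limit the exclusion to bleeding with onset up to and including the Week 52/EOT product collection. After that the protocol's ordinary rules apply: worsening relative to the pre-treatment condition is an adverse event, and return to the pre-existing state is not. With no volume available, that judgement will rest on the woman's report and the investigator's assessment, so the completion guidance should say so.
2. **SAP Section 9.1.** Tabulate heavy menstrual bleeding with post-treatment onset in a separate row, by parent study group.
3. **SAP Section 7.3.6.** Summarise MIQ item 1 at Follow-up by parent study group, showing separately the women whose menses has not returned.
4. **Protocol Section 6.6.1.5.** Reconcile the MIQ timing with the Schedule of Activities.

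The cost is one sentence in the protocol, site guidance, a clarification and two small tables. The MIQ is already scheduled at that visit, so no new assessment is added. The downside is a slightly less favourable adverse event count and some borderline calls between worsening and recurrence. The separate row keeps both visible and leaves the on-treatment counts unchanged.

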7.1.2. Serious Adverse Event

A serious adverse event is any untoward medical occurrence that, at any dose:

- a. Results in death;
- b. Is life-threatening;

NOTE: The term “life-threatening” in the definition of “serious” refers to an event in which the study participant was at risk of death at the time of the event. It does not refer to an event, which hypothetically might have caused death, if it were more severe. For example, drug-induced hepatitis that resolved without evidence of hepatic failure would not be considered life-threatening even though drug-induced hepatitis can be fatal.

- c. Requires hospitalization or prolongation of existing hospitalization;

NOTE: In general, hospitalization signifies that the patient has been detained at the hospital or emergency ward for observation and/or treatment that would not have been appropriate in the physician’s office or out-patient setting. Complications that occur during hospitalization are adverse events. If a complication prolongs hospitalization or fulfills any other serious criteria, the event is serious. When in doubt as to whether “hospitalization” occurred or was necessary, the adverse event should be considered serious. Hospitalization for elective treatment of a pre-existing condition that did not worsen from the Week 24/Baseline visit is not considered an adverse event.

- d. Results in persistent or significant disability/incapacity;

NOTE: The term disability means a substantial disruption of a person’s ability to conduct normal life functions. This definition is not intended to include experiences of relatively minor medical significance such as uncomplicated headache, nausea, vomiting, diarrhea, influenza, and accidental trauma (eg, sprained ankle), which may interfere or prevent everyday life functions but do not constitute a substantial disruption.

- e. Is a congenital anomaly/birth defect;
- f. Important medical events that jeopardize the patient and may require medical or surgical intervention to prevent one of the outcomes listed above. Examples of such events are invasive or malignant cancers, intensive treatment in an emergency room or at home for allergic bronchospasm, blood dyscrasias or convulsions that do not result in hospitalization, or development of drug dependency or drug abuse.

7.2. Adverse Event Reporting

The reporting of serious adverse events by the sponsor (Myovant Sciences GmbH) to regulatory authorities is a requirement and each authority has a timetable for reporting these events based upon established criteria. Likewise, it is the responsibility of the investigator to report serious adverse events to their local institutional review board (IRB) or institutional ethics committee (IEC).

Care will be taken not to introduce bias when detecting adverse events and/or serious adverse events. Open-ended and non-leading verbal questioning of the patient is the preferred method to inquire about adverse event occurrence. Appropriate questions include:

- “How are you feeling?”
- “Have you had any (other) medical problems since your last visit/contact?”
- “Have you taken any new medicines, other than those provided in this study, since your last visit/contact?”

The patient’s answers to study questionnaires will not be used as a primary means to collect adverse events, however they should be reviewed by the study site personnel and the study monitors. Should the investigator or site staff become aware of a potential adverse event through the information collected with these instruments, proper follow-up with the patient for medical evaluation should be undertaken. Through this follow-up, if it is determined that an adverse event not previously reported has been identified, normal reporting requirements should be applied.

All patients who experience an adverse event will be evaluated at appropriate time intervals until the event resolves or has stabilized or become chronic. At the conclusion of the study, the investigator and medical monitor will assess unresolved adverse events and determine if additional follow-up is warranted.

All adverse events, whether or not related to the study drug treatment, must be fully and completely documented on the adverse event case report form and in the patient’s source documents. In addition, any adverse event resulting in permanent treatment discontinuation must be recorded on the appropriate case report form as well as documented in the patient’s source documents. Adverse event terms should include a diagnosis, as available, in preference to listing the individual signs and symptoms. If the diagnosis is not known, the investigator should record each sign and symptom as an individual adverse event.

Overdose and pregnancy in the patient will be reported as described in [Section 7.7](#) and [Section 7.8](#), respectively.

